7.2 Daratumumab Preparation

Daratumumab-SC will be provided as a fixed-dose (1800 mg) which is a combination drug product containing rHuPH20 drug substance (2000 U/mL) and daratumumab drug substance (120 mg/mL) in a single vial.. Detailed instructions for preparation and administration of daratumumab will be supplied in the package insert.

Agent	Dose	Route	Days
CYCLE 1			
Daratumumab	1800 mg dose	SC	weekly (Days 1, 8, 15, 22)
CYCLE 2			
Daratumumab	1800 mg dose	SC	weekly (Days 1, 8, 15, 22)
Ibrutinib	420 mg QD	Oral	1-28
CYCLE 3-6			
Daratumumab	1800 mg dose	SC	every 2 weeks (Days 1, 15)
Ibrutinib	420 mg QD	Oral	1-28

CYCLE 7-and 24			
Daratumumab	1800 mg dose	SC	every 4 weeks (Day 1)
Ibrutinib	420 mg QD	Oral	1-28
Cycle length = 28 days (±4 days)			
# For patients in Cohort 1, ibrutinib will be stopped for at least 1 week prior (washout period) prior to initiating C1 (daratumumab alone). Subjects treatment until PD			

7.3 Dosing schedule and duration:

Daratumumab (1800 mg) will be administered by SC injection by manual push over approximately 3 – 5 minutes in the abdominal subcutaneous tissues in the left/right locations, alternating between individual doses. The volume of the SC solution will be 15 mL for the 1800 mg dose. Reasons for continued observation on subsequent daratumumab injection may include but are not limited to the following: subjects with a higher risk of respiratory complications (e.g., subjects with mild asthma or subjects with COPD who have an FEV1 < 80% at screening or developed FEV1 < 80% during the study without any medical history), subjects with IRR with the first injection of study drug, subject with decreased condition on day of dosing compared to prior dosing day. The dose of daratumumab will remain constant throughout the study..

Dara-SC Dosing:

Dara-SC dosing schedule (whether in combination or monotherapy)

Weeks	Schedule
Weeks 1 to 8	Weekly (total of 8 doses)
Weeks 9 to 24 ^a	Every two weeks (total of 8 doses)
Week 25 and onward until PD ^b	Every four weeks

^a First dose of the every-2-week dosing schedule is given at Week 9

^b First dose of the every-4-week dosing schedule is given at Week 25

All daratumumab administrations will be in an outpatient setting. Subjects will receive pre injection medications and post-injection medication as outlined in Section 7.5.

Vital signs should be monitored extensively on Cycle 1 Day 1 before, and after the first administration of daratumumab. For all other administrations, vital signs should be measured before the start of injection and at the end of the injection. If the subject experiences any significant medical event, then the investigator should assess whether the subject should stay overnight for observation. If the subject has not experienced a significant medical event but is hospitalized overnight only for observation, then the hospitalization should not be reported as an SAE.

If an IRR develops, then the injection should be temporarily interrupted or slowed down. In the event of a life-threatening IRR (which may include pulmonary or cardiac events) or anaphylactic reaction, dara-SC should be discontinued, and no additional dara-SC should be administered to the participant. See Section 7.6 for instructions on the management of IRR and local ISRs.

7.5 Guidelines for Prevention of Infusion Reactions

All participants will receive the following medications 1 to 3 hours prior to each study drug administration:

Pre-Dose Medication:

- An antipyretic: paracetamol (acetaminophen) 650-1000 mg IV or PO
- An antihistamine: diphenhydramine 25-50 mg IV or PO or equivalent. Avoid IV use of promethazine.
 - After Cycle 6, if a participant has not developed an infusion-related reaction and is intolerant to antihistamines, modifications are acceptable as per investigator discretion.
- Corticosteroids (Long-acting or intermediate-acting):
 - *Monotherapy:* Methylprednisolone 100 mg, or equivalent, administered intravenously. Following the second infusion, the dose of corticosteroid may be reduced (oral or intravenous methylprednisolone 60 mg or equivalent).
 - If the subject does not experience a major systemic administration-related reaction after the first 3 doses, consider discontinuing the administration of corticosteroids (excluding any background regimen-specific corticosteroid).

Pre-dose administration of a leukotriene inhibitor (montelukast 10 mg PO or equivalent) is optional in Cycle 1 Day 1 and can be administered up to 24 hours before infusion as per investigator discretion.

If necessary, all PO pre-infusion medications may be administered out of the clinic on the day of the infusion, provided they are taken within 3 hours before the infusion.

Post-infusion Medication -

Administer post-infusion medication to reduce the risk of delayed infusion related reactions as follows:

- *Monotherapy studies:*
 - In an effort to prevent delayed infusion-related reactions, all participants will receive long- or intermediate-acting corticosteroid orally (20 mg methylprednisolone or equivalent in accordance with local standards) on the 2 days following all daratumumab infusions (beginning the day after the infusion).
 - In the absence of infusion related AEs after the first 3 infusions, post-infusion corticosteroids should be administered per investigator discretion.
- *Combination therapy:*
 - Consider administering low-dose methylprednisolone (≤ 20 mg) or equivalent, the day after the infusion. However, if a background regimen-specific corticosteroid (e.g. dexamethasone) is administered the day after the infusion, additional post-infusion steroids are not required, but may be considered by the investigator.
 - For participants with a higher risk of respiratory complications (e.g. participants with mild asthma or participants with COPD who have an FEV1 $< 80\%$ at screening or developed FEV1 $< 80\%$ during the study without any medical history) the following post-infusion medication should be considered:
 - Antihistamine (diphenhydramine or equivalent)
 - Leukotriene inhibitor (montelukast or equivalent)
 - Short-acting $\beta 2$ adrenergic receptor agonist such as salbutamol aerosol
 - Control medications for lung disease (e.g. inhaled corticosteroids \pm long-acting $\beta 2$ adrenergic receptor agonists with asthma; long-acting

bronchodilators such as tiotropium or salmeterol ± inhaled corticosteroids for participants with COPD)

- In addition, these at-risk participants may be hospitalized for monitoring for up to 2 nights after daratumumab administration. If participants are hospitalized, then an improvement in FEV1 should be performed and documented prior to discharge. If these participants are not hospitalized, then a follow-up telephone call should be made to monitor their condition within 48 hours after all infusions. If the participant has not experienced a significant medical event but is hospitalized overnight only for observation, then the hospitalization should not be reported as a serious adverse event. Investigators may prescribe bronchodilators, H1-antihistamines, and corticosteroids that are deemed necessary to provide adequate supportive care in the event a bronchospasm occurs after participants are released from the hospital/clinic. If an at-risk participant experiences no major infusion-related reactions, then these post-infusion medications may be waived after 4 doses at the investigator's discretion.
- Any post-infusion medication will be administered after the infusion has completed.

7.6 Management of Infusion-related Reactions and Local Injection-site Reactions of Daratumumab-SC

Infusion-related Reactions (IRRs):

Infusion-related reactions (IRRs) are systemic reactions related to daratumumab administration. Participants should be observed carefully during daratumumab administrations. Trained study staff at the clinic should be prepared to intervene in case of any IRRs, and resources necessary for resuscitation (e.g., agents such as epinephrine and aerosolized bronchodilator, also medical equipment such as oxygen tanks, and a defibrillator) must be available. Attention to staffing should be considered when multiple subjects will be dosed at the same time. If an infusion-related reaction develops during Dara SC administration, then the administration should be temporarily interrupted. Subjects who experience adverse events during daratumumab SC administration must be treated according to the investigator's judgment and best clinical practice. The following guidelines may apply: (a) Subjects should be treated with acetaminophen, antihistamine, or corticosteroids. Intravenous saline may be indicated. For bronchospasm, urticaria, or dyspnea, subjects may require antihistamines, oxygen, corticosteroids, or bronchodilators. For hypotension, subjects may require vasopressors. (b) In the event of a life-threatening infusion-related reaction (which may include pulmonary or cardiac events), or anaphylactic reaction, daratumumab should be discontinued and no additional daratumumab should be administered to the subject.

7.7 Administration-Related Events of Grade 1 or Grade 2:

If the investigator assesses a Grade 1-2 IRR to be related to the daratumumab administration, then the Dara-SC administration should be interrupted. When the subject's condition is stable, Dara-SC administration may be restarted at the investigator's discretion. Refer to the USPI for further details regarding continuation of Dara-SC administration.. If the subject experiences a Grade 2 or higher event of laryngeal edema or a Grade 2 or higher event of bronchospasm that does not respond to systemic therapy and does not resolve \leq 6 hours from the onset, then the subject must be permanently discontinued from Dara-SC treatment..

7.8a Administration-Related Reactions of Grade 3 or Higher:

For infusion-related adverse events that are Grade 4, the Dara-SC administration must be stopped and treatment with daratumumab will be permanently discontinued for that subject. For infusion-

- Patients will be evaluated for response after first 4 weeks (or later if completion of cycle 1 is delayed) of single agent daratumumab (completed Cycle 1) and thereafter every 2 treatment cycles of combination therapy.
- MRD status will be recorded every 3 cycles (as discussed previously in Section 4.0, see detailed MRD section 11.3).

7.9c Treatment by Local Medical Doctor (LMD):

Patient will need to return to Mayo Clinic for every treatment cycle for daratumumab therapy. If patient stop treatment and is on follow-up this can be done in conjunction with patients' primary medical doctor.

7.9d Return to treating institution

For this protocol, the patient must return to the consenting institution for evaluation and drug

administration at least every 28 days during treatment for the first 6 cycles. After the first 7 cycles, patients may elect to return every 3 cycles per treating MD's discretion as long as there are no active ongoing toxicities that have not returned to baseline. Clinical evaluation and blood tests can be obtained per test schedule and mailed/faxed to the consenting institution and patient can return at least every 3 cycles for follow up to the consenting institution. The cycle length will remain at 28 days and data collection forms will be due at the end of each cycle. Adverse events and adherence to study treatment will be collected at the end of each cycle by telephone call for cycles where the patient does not return to the clinic. The patient should retain the pill diaries and medication bottles (even if unopened or empty) along with any unused pills for each cycle and bring them to their next visit so that dosing can be recorded on the evaluation/treatment forms for each cycle.

8.0 Dosage Modification Based on Adverse Events

An evaluation of potential treatment-induced toxicity in patients with CLL can be difficult. Moreover, some conventional criteria are not applicable to studies involving patients with hematologic malignancies in general and CLL in particular. An example is hematologic toxicity: patients with advanced CLL may exhibit deterioration in blood counts which may represent either treatment-related toxicity or progressive bone marrow failure from disease itself. Toxicity grades below are described using the NCI Common Terminology Criteria for Averse Events (CTCAE) version 5.0.

8.1 Dose Levels (Based on Adverse Events in Tables 8.2 and 8.3)

Dose Level	Ibrutinib
1*	420 mg daily
-1	280 mg daily
-2	140 mg daily

*Dose level 1 refers to the starting dose.

NOTE: If either of Daratumumab or Ibrutinib is discontinued, the patient can continue on the other drugs, unless specified otherwise in the dose modification tables. If both are discontinued, the patient will go to survival follow-up (Section 4.2). No dose modifications are allowed for daratumumab

→ → Use the NCI Common Terminology Criteria for Adverse Events (CTCAE) current version 5.0* unless otherwise specified ← ←

*Located at [REDACTED]

8.2 Dose Modifications

Any dose/dosage adjustment must be overseen by medically qualified study site personnel (principal or subinvestigator sub-investigator) unless an immediate safety risk appears to be present.

Daratumumab Subcutaneous

Individual dose modification of Dara SC is not permitted. For managing Dara SC-related toxicities, either a dose interruption or a dose delay is recommended. ONLY if any of the

following criteria are met and the event cannot be ascribed to lenalidomide, bortezomib, dexamethasone, carfilzomib (if applicable) or underlying MM, the Dara SC administration must be held to allow for recovery from toxicity. The criteria for a dose delay are:

- Grade 4 hematologic toxicity (except for Grade 4 lymphopenia)
- Grade 3 or higher thrombocytopenia with bleeding
- Febrile neutropenia of any grade
- Grade 4 Neutropenia with any grade infection
- Grade 3 or higher nonhematologic toxicities with the following exceptions:
 - Grade 3 nausea that responds to antiemetic treatment within 7 days
 - Grade 3 vomiting that responds to antiemetic treatment within 7 days
 - Grade 3 diarrhea that responds to antidiarrheal treatment within 7 days
 - Grade 3 fatigue that was present at baseline or that lasts for <7 days after the last administration of Dara SC
 - Grade 3 asthenia that was present at baseline or that lasts for <7 days after the last administration of Dara SC

Administration of Dara SC may be restarted upon recovery from toxicity to Grade 2 or baseline, with the exception that Grade 2 laryngeal edema or Grade 2 bronchospasm must be fully recovered.

If Dara SC administration does not commence within the prespecified window (Table 8.3) of the scheduled administration date, then the dose will be considered a missed dose.

Administration may resume at the next planned dosing date. A missed dose will not be made up.

Table 8.3 Dara SC-related Toxicity Management (28-day Cycles)

Cycles	Frequency	Missed Dose	Dosing Resumption
1-2	Weekly	>3 days	Next planned weekly dosing date
3-6	Every 2 weeks	>7 days	Next planned every 2-week dosing date
7-24	Every 4 weeks	> 14 days	Next planned every 4-week dosing date

Abbreviation: SC=subcutaneous; TE=transplant eligible.

If a dose is delayed, then the dates of all subsequent doses must be adjusted. Any AE deemed to be related to Dara SC that requires a dose hold of more than 28 days will be evaluated by the investigator to determine if further dosing will be safe and efficacious.

Subjects who miss ≥ 3 consecutive planned doses of daratumumab for reasons other than toxicity will be withdrawn from treatment, unless, upon consultation with the sponsor and the review of safety and efficacy, continuation is agreed upon.

Ibrutinib

CTCAE System/Organ/Class (SOC)	ADVERSE EVENT	AGENT	ACTION**
Blood and lymphatic system disorders	≥ Grade 3 Febrile neutropenia	Ibrutinib	Hold (day 1) or omit (days 2-28) Ibrutinib until fever resolves and ANC \geq 1000/ μ L, then resume Ibrutinib at the previous dose.
Gastrointestinal disorders	≥ Grade 3 Nausea (if persistent despite optimal antiemetic therapy)	Ibrutinib	Hold (day 1) or omit (days 2-28) Ibrutinib until recovery to Grade \leq 1 or baseline; may restart at original dose for first occurrence. Each subsequent occurrence may restart at next lower dose after recovery to Grade \leq 1 or baseline. If AE occurs at lowest dose discontinue treatment.
	≥ Grade 3 Vomiting (if persistent despite optimal antiemetic therapy)		
	≥ Grade 3 Diarrhea (if persistent despite optimal anti-diarrheal therapy)		
Investigations	Neutrophil count decreased Grade 4 lasting $>$ 7 days	Ibrutinib	Hold (day 1) or omit (days 2-28) Ibrutinib until recovery to Grade \leq 1 or baseline; may restart at original dose for first occurrence. Each subsequent occurrence may restart at next lower dose after recovery to Grade \leq 1 or baseline. If AE occurs at lowest dose discontinue treatment. NOTE: Baseline cytopenia: In patients whose baseline (i.e., prior to starting protocol therapy) ANC is 1000/ μ L, the above Ibrutinib dose modifications, if required, would not be applied until Cycle 3.
Other non-hematologic	Any other Grade 4 AE or any unmanageable Grade 3 AE	Ibrutinib	Hold (day 1) or omit (days 2-28) Ibrutinib until recovery to Grade \leq 1 or baseline; may restart at original dose for first occurrence. Each subsequent occurrence may restart at next lower dose after recovery to Grade \leq 1 or baseline. If AE occurs at lowest dose discontinue treatment.

** Use the following to describe actions in the Action column:

- **Omit** = The current dose(s) for the specified drug(s) during a cycle is skipped. The patient does not make up the omitted dose(s) at a later time.
- **Hold/Delay** = The current dose(s) of all drugs during a cycle is delayed. The patient does make up the delayed dose(s) when the patient meets the protocol criteria to restart drugs.
- **Discontinue** = The specified drug(s) are totally stopped.

Dose delay: Ibrutinib may be held for toxicity considerations for a maximum of 28 consecutive days. Study medication should be discontinued permanently in the event of a toxicity lasting more than 28 days. If Ibrutinib is interrupted for a reason other than toxicity (e.g. unrelated illness) it must be restarted \leq 60 days. If interrupted for more than 60 days, study medication should be discontinued permanently and go to survival follow-up.

- **Dose re-escalation:** Patients who require a dose reduction during a given cycle will remain at that dose for at least 2 additional cycles. **At the investigator discretion, the dose of ibrutinib may be re-escalated after 2 cycles of a dose reduction in the absence of a recurrence of the toxicity that led to this reduction.** This is particularly reasonable based upon the long-term safety data now available in ibrutinib treated patients that show that most of the hematological or non-hematological AEs either decreased or remained stable (see investigator brochure section 5.3).
- If multiple adverse events are seen, administer dose based on the greatest reduction required by any single adverse event observed.
- Dose modifications are for adverse events attributed to study treatment only. Dose modifications are not required for adverse events if they are deemed unrelated to study treatment.
- Reductions apply to treatment given in the preceding cycle and are based on adverse events observed since the prior dose.
- If cough, dyspnea, and other pulmonary symptoms occur, a chest x-ray and high-resolution chest CT scan should be obtained. Incentive spirometry studies (to include DLCO) should be considered. Consider Pneumocystis pneumonia or viral pneumonitis

8.3 Dose Modification for Hematological Toxicities (Platelet and Hemoglobin only)

Note: hematological toxicity is not based on CTCAE 5.0 except neutrophil, but based on CLL specific hematological toxicity (this table and Appendix V).

Dose modification guidelines for drug-related hematological (hemoglobin and platelets) adverse events						
Toxicity	Grade ^{1, 2}	Decrease from pretreatment	Hold Treatment (Y/N)	Timing for restarting treatment	Dose/Schedule for restarting treatment	Discontinue Subject (after consultation with PI)
CLL/NHL specific Hematological Toxicity (Appendix V)	1	11-24% decrease in HGB or PLT	No	N/A	N/A	N/A
	2	25-49% decrease in HGB or PLT				
	3	50-74% decrease in HGB or PLT	Yes	Toxicity resolves to Grade 0-1 or baseline	Hold (day 1) or omit (days 2-28) Ibrutinib until recovery to Grade ≤ 1 or baseline; may restart at original dose for first occurrence. Each subsequent occurrence may restart at next lower dose after recovery to Grade ≤ 1 or baseline. If AE occurs at lowest dose, discontinue treatment.	Toxicity does not resolve within 8 weeks of last treatment Permanent discontinuation should be considered for any severe or life-threatening event. Go to event monitoring if ≥ 1 cycles of therapy was given.
	4	$\geq 75\%$ decrease in HGB or PLT	Yes	Toxicity resolves to Grade 0-1 or baseline		

¹If, at any level of decrease the platelet count is $< 20,000/\mu\text{L}$, this will be considered grade 4, unless the initial platelet count was $\leq 20,000 \mu\text{L}$ in which case the patient is invaluable for toxicity referable to platelet counts.

²If, at any level of decrease from the baseline value the platelet and/or hemoglobin counts are within normal limits, this will be considered a grade 0.

9.0 Ancillary Treatment/Supportive Care

9.1 Growth factors

Use of neutrophil growth factors (filgrastim and pegfilgrastim) or red blood cell growth factors (erythropoietin) is permitted per institutional policy and in accordance with the ASCO guidelines. They should be utilized as clinically warranted and following institutional policies and recommendations. Growth factors can be used during the treatment cycle as clinically indicated. The use of growth factors should follow published guidelines of the American Society of Clinical Oncology. Update of Recommendations for the Use of Hematopoietic Colony-Stimulating Factors: Evidence- Based, Clinical Practice Guidelines.

9.2 Supportive care:

Patients should receive full supportive care, including transfusions of blood and blood products, antibiotics, and antiemetics when appropriate. (A) Any blood transfusions administered must be irradiated blood products to reduce risk of transfusion- mediated graft versus host disease in CLL patients receiving T-cell suppressive therapy. Leukocyte reduction of all blood products for patients on protocol is also required. All blood products and concomitant medications such as antidiarrheals, analgesics, and/or antiemetics received from the first day of study treatment administration until 30 days after the final dose will be recorded in the medical records. (B) Antiemetics may be used at the discretion of the attending physician. (C) Prophylactic antibiotics and antifungals may be prescribed at the treating physicians' discretion and as clinically indicated, or as per the institutional guidelines. (D) Treatment for autoimmune cytopenias are permitted for <14 days at doses that do not exceed 100 mg per day of prednisone or equivalent. (E) Supportive medications in accordance with standard practice (such as for emesis, diarrhea, etc.) are permitted. (F) Short courses (≤ 14 days) of steroid treatment for non-cancer related medical reasons (e.g., joint inflammation, asthma exacerbation, rash, antiemetic use and infusion reactions) at doses that do not exceed 100mg per day of prednisone or equivalent are permitted.

9.3 Tumor Lysis Syndrome (TLS) prophylaxis and treatment:

Patients who are at risk of TLS as determined by the treating physician, may receive Allopurinol 300 mg/day (or an equivalent standard agent for prevention of hyperuricemia) orally for the first two weeks of the first cycle of protocol therapy. Allopurinol may be continued after the first two weeks at the investigator's discretion and as clinically indicated. Subjects should be observed closely for signs and symptoms of TLS during the initial cycle of therapy. Subjects should be encouraged to drink an abundant amount of fluid prior to treatment. Subjects should maintain adequate hydration and urine output.

9.4 Treatment related lymphocytosis:

Lymphocytosis has been reported with ibrutinib, however since in this clinical trial patient will have received daratumumab prior to initiating the ibrutinib it is not known if this lymphocytosis will still happen upon treatment with ibrutinib. Patients who develop this reaction will be monitored as per standard clinical protocol without specific intervention unless other specific symptoms / signs of disease progression is noted (such as increase in lymph node size that is progressive and persist beyond 3 months of therapy, worsening of cytopenia from the time of initiation of therapy that is considered to be due to progressive disease and is consistent with the IWCLL guidelines requiring therapeutic intervention, development of B symptoms persisting for more than 2 months while on therapy or other factors such as organomegaly demonstrating disease progression).

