7.0 Protocol Treatment

Overall Treatment Schedule: Overall treatment schedule (for both Cohorts) include patient receiving Daratumumab SC alone in C1 followed by addition of ibrutinib to daratumumab starting C2 (and onwards). For patients already on BTK inhibitor who are entering Cohort 1, BTK inhibitor will be stopped (see also note below for more detailed clarification) for at least 1 week prior (washout period) to initiating C1 (daratumumab alone). Once these patients have completed the C1, ibrutinib will be started as part of the combination regimen starting C2.

Note: Treatment can be initiated/continued independent of disease activity during the washout period i.e. if the disease is progressing while on Daratumumab alone. Also, given the clinical course of patients resistant to BTK inhibitor can be rapid, if in treating physician opinion stopping the BTK inhibitor can impact adversely patient's disease course than patient may continue the BTK inhibitor up until starting study treatment and then Ibrutinib plus daratumumab will be started in lieu of BTK inhibitor. In such a case, Cycle 1 will have both ibrutinib + Daratumumab. The schedule and dosing of Daratumumab will follow the same design as noted in 7.2. This, however must be approved by the Principal Investigator [REDACTED] of the study protocol.

Duration of treatment: Patient will be treated as indicated in section 7.0, unless they have progressive disease or unacceptable toxicity. Patients who complete treatment per protocol will continue to the end of treatment visit and then, survival follow-up.

DARATUMUMAB

7.1 Daratumumab Subcutaneous schedule (Cycle length = 28 days, ± 4 days):

- **Cycle 1 & 2:** Daratumumab SC alone (1800 mg dose) weekly (Days 1, 8, 15, 22 of each cycle).
- **Cycle 3-6:** Daratumumab SC (1800 mg dose) will be given every 2 weeks (Days 1, 15 of each cycle).
- **Cycle 7 onwards:** Daratumumab SC (1800 mg dose) will be given every 4 weeks (Day 1 of each cycle).

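### Section 9.3 directs close TLS observation only in the initial cycle, by default daratumumab alone, so it ends as ibrutinib starts; general provisions cover Cycle 2 only in part (low severity, cheap to fix)

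*Combined protocol and SAP*

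**What the plan says.** **TLS provisions (section 9.3).** The directive is "Subjects should be observed closely for signs and symptoms of TLS during the initial cycle of therapy". Patients whom the treating physician considers at risk may receive allopurinol "orally for the first two weeks of the first cycle of protocol therapy". After that, "Allopurinol may be continued after the first two weeks at the investigator's discretion and as clinically indicated". Hydration advice follows with no cycle limit: "Subjects should maintain adequate hydration and urine output".

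**Treatment sequence (section 7.0).** Both cohorts receive daratumumab alone in Cycle 1, "followed by addition of ibrutinib to daratumumab starting C2 (and onwards". Section 7.9a puts the first ibrutinib dose on Day 1 of Cycle 2, and the 7.2 table agrees. There is one exception. A patient already on a BTK inhibitor, for whom stopping it is judged harmful, may with Principal Investigator approval go straight to the combination: "In such a case, Cycle 1 will have both ibrutinib + Daratumumab".

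**Visits (section 7.2).** Daratumumab in Cycles 1 and 2 is given "weekly (Days 1, 8, 15, 22" of the 28-day cycle. Section 7.3 asks for vital signs before and at the end of each injection.

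**Laboratory schedule (section 4.1, footnote 5).** Cycle 1 Day 15 chemistry is at the physician's discretion, with TLS risk named as one reason. TLS monitoring is described as standard of care, with no cycle stated. From Cycle 2, chemistry is drawn before each cycle, and anything further is as clinically indicated.

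**Listed toxicities.** Section 15.27 names TLS for ibrutinib twice, once in the 1% to 10% list and once among important or life-threatening events. Section 15.17, for daratumumab, does not name it.

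**The concern.** The only sentence that tells staff to watch closely for TLS is tied to a cycle in which most patients are not yet taking the drug with the listed TLS risk. Followed as written, it stops when that drug is added. Section 9.4, which comes next, does allow for the staggered start in discussing lymphocytosis, "since in this clinical trial patient will have received daratumumab prior to initiating the ibrutinib". Section 9.3 does not, and the protocol gives no reason for ending close observation before ibrutinib.

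What is at stake is patient safety during the first weeks of ibrutinib, mainly in BTK-inhibitor-naive Cohort 2, for whom Cycle 2 is the first exposure to the class. It has no bearing on the primary analysis.

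**Working it through.** The plan gives no figure to reproduce on this point, so the check sets the sections side by side.

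1. **Which cycle is the initial cycle?** One could read 9.3 as meaning the first cycle of each drug. The allopurinol sentence in the same paragraph refers to the first cycle of protocol therapy, so the natural reading is protocol Cycle 1.

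2. **What is given in that cycle?** Daratumumab alone by default (7.0, 7.2). Section 7.1 groups Cycles 1 and 2 as daratumumab alone, but it sets out only the daratumumab schedule. Sections 7.0, 7.2 and 7.9a agree that ibrutinib starts in Cycle 2.

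3. **For which drug is TLS listed?** In section 15, only ibrutinib. That does not show daratumumab to be free of TLS risk in CLL: 15.17 defers to the Investigator's Brochure and package insert, and section 1.3 says daratumumab has not been studied clinically in CLL. The Cycle 1 provisions are therefore reasonable.

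4. **What reaches Cycle 2?**

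| Provision | Reaches Cycle 2? | Directs TLS observation after the first ibrutinib dose? |
|---|---|---|
| 9.3 close observation | No, initial cycle only | No |
| 9.3 allopurinol | Only if continued at discretion | No |
| 9.3 hydration | Yes | No |
| Footnote 5, standard of care | Yes, no cycle limit | Not specifically |
| Footnote 5, pre-cycle chemistry (includes uric acid, phosphorus, potassium, LDH, creatinine) | Yes | No; the pre-Cycle 2 panel precedes the dose |
| Footnote 5, further tests | Yes, at discretion | No |
| 7.3 vital signs at daratumumab visits | Yes | No |
| 15.29 nursing note on renal function and uric acid | Yes, no timing given | No, TLS not named |

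5. **Existing contact.** With the first ibrutinib dose on Cycle 2 Day 1, the later daratumumab visits in that cycle fall 8 − 1 = 7, 15 − 1 = 14 and 22 − 1 = 21 days after it.

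6. **Patients concerned (section 16.12).** Cohort 2: 26 evaluable + 2 extra = 28. Cohort 1: 22 + 2 = 24. Total: 28 + 24 = 52, the stated maximum accrual. These are accrual ceilings, not treated counts. The extra places allow for ineligibility and cancellation, among other reasons, and section 13.6 defines a cancelled patient as one who received no study treatment. Losses during Cycle 1 lower the Cycle 2 number further. The documents do not say how many in either cohort will start ibrutinib in Cycle 2; the possible ranges are 0 to 28 in Cohort 2 and 0 to 24 in Cohort 1.

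**The case against.** The strongest reply is that Cycle 2 is already largely looked after. TLS monitoring is standard of care throughout, the physician may order chemistry or continue allopurinol, and patients are seen weekly with vital signs. Treatment starts at one specialist centre under a medical oncologist (6.4). Ibrutinib is a commercial drug whose package insert, to which 15.27 refers, may contain its own advice; that cannot be checked here. The ibrutinib safety account in section 1.2 does not discuss TLS, which appears only as a term in the 15.27 lists. Much of this stands, and it is why the point is minor. It does not remove the mismatch: the same standard of care applies in Cycle 1, where the protocol still saw fit to write a specific directive.

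Three stronger readings are tempting and should not be drawn.

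- **That there is no TLS monitoring in Cycle 2.** The table above shows otherwise.
- **That Cycle 2 has a chemistry gap of its own.** The pre-Cycle 2 and pre-Cycle 3 panels are about 28 days apart (24 to 32 with the ±4-day window). But Cycle 1 Day 15 chemistry is also discretionary, so the interval between obligatory panels is a feature of the schedule in both cycles. Cycle 1 differs only in the observation directive, the default allopurinol window and the named Day 15 option.
- **That 1% to 10% is a TLS rate from which expected events can be computed.** It is the heading of a long mixed list that also contains pulmonary tuberculosis and legionella pneumonia. It is not a rate for each entry, nor for this population or schedule.

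**Conclusion.** The point holds as a low-severity safety improvement that could be made. The explicit close-observation directive and the default allopurinol window are timed to protocol Cycle 1, and under the default schedule they do not extend to the start of ibrutinib. General and discretionary provisions cover Cycle 2 in part.

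It applies mainly to Cohort 2. Cohort 1 patients have had a BTK inhibitor before, and those using the 7.0 exception receive ibrutinib within the observed cycle. The size of any harm cannot be derived from the documents, and many physicians may monitor in Cycle 2 anyway.

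The conclusion assumes that the initial cycle means protocol Cycle 1 and rests on the toxicity lists in section 15 alone; the Investigator's Brochures and package inserts were not available.

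**What to change.** Keep the Cycle 1 provisions. Add one sentence to 9.3, for example: *Close observation for TLS, and the assessment of TLS risk and need for allopurinol, also apply in the first cycle that contains ibrutinib (Cycle 2 by default; Cycle 1 under the exception in section 7.0), using the weekly daratumumab visits already planned.*

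Naming TLS risk in footnote 5 as a reason for a chemistry draw early in that cycle, at Day 8 or Day 15, is optional. It would only make explicit what the footnote already permits.

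The cost is one sentence, slightly more observation and, for patients judged at risk, possibly allopurinol or a chemistry draw at an existing visit. No visit is added, and the analysis plan does not change.
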